#### 9.5.1.1 PCR-corrected ACPR and uncorrected ACPR

At each visit, the mean ACPR rate with 95% confidence intervals will be provided using Pearson-Clopper method for each treatment group.

Data will be handled as follows:

- Treatment failures after 7 days (i.e., Day 8) due to reinfection based on PCR genotyping are not considered as failure for PCR-corrected analyses.
- For parasitological uncorrected ACPR, patients will be treated as failure on and after the visit when a new infection (i.e., reinfection) with *P. falciparum* or other species is detected.
- Patients who received rescue medication for the treatment of *P. falciparum* malaria (except for the treatment of a new infection) will be considered treatment failures (from the day of rescue use onwards). Patients who received other concomitant medication having an effect on malaria for reasons other than rescue therapy e.g. for the treatment of *P. vivax* or for the treatment of *P. falciparum* gametocytes (e.g. primaquine, certain

antibiotics (sulfonamides, tetracycline, etc.) will be considered in the analysis as if they had not taken the drug.

- Patients will be counted as failure at a visit (e.g., Day 15, etc.) if (a) they did not have a parasite count at that visit unless these patients could be classified as cured based on absence of parasitaemia at a later time (e.g., Day 29), or (b) they did not have valid PCR evaluations at baseline and the visit if parasitaemia was present at that time (e.g., Visit Day 15).

In addition, PCR-corrected ACPR rate will be calculated and plotted using the Kaplan-Meier method for each treatment group in the FAS (see [Section 9.4.4](#)).

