2.1.1.1 Definition of treatment failures

Early Treatment Failures (ETF)

Patient will be classified as ETF upon meeting any of the following criterion

- Development of danger signs or severe malaria on Day 2, Day 3, Day 4 in the presence of parasitemia.
- Parasitemia on Day 3 higher than Day 1 count irrespective of axillary temperature.
- Parasitemia on Day 4 with axillary temperature $\geq 37.5^{\circ}\text{C}$.
- Parasitemia on Day 4 equals to or more than 25% of count on Day 1.

Late Clinical Failure (LCF)

Patient will be classified as LCF upon meeting any of the following criterion

- Development of danger signs or severe malaria on any day from Day 5 to Day 43 in the presence of parasitemia without previously meeting any of the criteria of early treatment failure.
- Presence of parasitemia and axillary temperature $\geq 37.5^{\circ}\text{C}$ on any day from Day 5 to Day 43 without previously meeting any of the criteria of Early Treatment Failure.

Late Parasitological Failure (LPF)

- Presence of parasitemia on any day from Day 8 to Day 43 and axillary temperature $< 37.5^{\circ}\text{C}$ without previously meeting any of the criteria of Early Treatment Failure or Late Clinical Failure. Missing body temperature assessment in presence of parasitemia will be classified as LCF.

Note: If the temperature is measured using other routes, such as oral/tympanic/rectal, the corresponding threshold for fever is 38.0°C . Danger signs or severe malaria is recorded as adverse events. The adverse event start date of danger signs or severe malaria will be used in the determination of ETF and LCF. Only *P. Falciparum* asexual form is used for parasitemia/parasite in the assessments of treatment failure and ACPR in [Section 2.1.1.2](#) below. The body temperature assessment closest to the blood smear assessment date will be used.

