2.1.1.2 Definition of ACPRs

Uncorrected ACPR at Day X where X=15, 29, or 43

- A patient is considered as non-responder at Day X if the patient experiences an ETF, LCF from Day 5 to Day X, or LPF from Day 8 to Day X.
- A patient is also considered as non-responder if the parasite is not cleared by Day X unless the patient discontinues the study prior to Day X without ETF or LCF or LPF, in which case the response is considered as missing.
- A patient is considered as responder (Uncorrected ACPR) at Day X if the patient is not classified as a non-responder at Day X and the patient has a malaria blood film showing absence of parasite at Day X or later if Day X is missing.
- The response for a patient is considered as missing/underdetermined if the patient is not classified as a non-responder and the malaria blood film result at Day X is missing and not followed by a subsequent negative result.

PCR-corrected ACPR at Day X where X=15, 29, or 43

- A patient is considered as non-responder at Day X if the patient experiences an ETF or LCF from Day 5 to Day 7.
- A patient is also considered as non-responder if the parasite is not cleared by Day X unless the patient discontinues the study prior to Day X without ETF or LCF or LPF, in which case the response is considered as missing,
- A patient is considered as non-responder at Day X if the patient has a parasite recrudescence from Day 8 to Day X
- A patient is considered as responder (corrected ACPR) at Day X if the patient is not classified as a non-responder by Day 7 and has a new infection or negative results from Day 8 to Day X based on PCR genotyping unless that the patient did not have parasites cleared prior to the new infection, in which case the patient is considered as non-responder.
- A patient is considered as responder at Day X if the patient is not classified as a non-responder at Day X and the patient has a malaria blood film showing absence of parasite at Day X or later if Day X is missing.
- The response for a patient is considered as missing/underdetermined if
 - The patient, not classified as non-responder at Day X, has parasite present from Day 8 to Day X for which the PCR genotyping of recrudescence or new infection is not determined.
 - The patient is not classified as a non-responder at Day X and the malaria blood film result at Day X is missing and not followed by a subsequent negative result.

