2.5.4.2 Analysis of uncorrected ACPR rate using Kaplan-Meier method

For the FAS, the proportion of patients with uncorrected ACPR at Day 29 and 95% CI will be also estimated using the Kaplan-Meier method ([Stepniewska and White 2006](#) and [WHO 2015](#))

Event = PCR-uncorrected non-responder during the study (same as at Day 15, Day 43, See [Section 2.1](#)). The event time is the first time when the patient becomes a non-responder without PCR-correction. If a patient parasite is not cleared at all, Day 7 is considered as the event time.

The uncorrected ACPR rate at Day 29 is estimated by the survivor function at Day 29.

Rule for censoring:

The following censoring rules will be applied to the patients who were not non-responders

- Patients who cleared the initial infection by Day 7 and are re-infected with species different than *P. Falciparum* will be censored at the time of re-infection.
- Patients who received non-rescue anti-malaria medication will be censored at the first time of anti-malaria medication;
- other patients will be censored at the time of last parasitemia assessment.

An asymptotic two-sided 95% CI for the difference in proportion of responders between each KAF156/LUM-SDF combination treatment group and Coartem[®] will be calculated from the z-test statistic distribution based on the variance of individual proportion using the Greenwood formula.

The confidence interval will be constructed as: $(r_k - r_c) \pm Z_{\alpha/2} * SE_d$,

where,

I_T = Kaplan-Meier estimate for the investigational group at time t,

I_C = Kaplan-Meier estimate for the control group at time t,

$SE_d = \sqrt{(SE_k^2 + SE_c^2)}$,

SE_T = estimated standard error for the investigational group based on Greenwood's formula,

SE_C = estimated standard error for the control group based on Greenwood's formula,

$Z_{\alpha/2}$ = z-statistic = $\text{probit}(1 - \alpha/2)$ from a normal distribution function,

$\alpha = 0.05$.

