2.7.2.1 PCR-corrected ACPR and uncorrected ACPR

At each visit, the ACPR rate with 95% confidence intervals will be provided using Pearson-Clopper method for each treatment group.

Handling of missing values/censoring/discontinuations

Data will be handled as follows for ACPRs (PCR corrected or uncorrected):

- Presence of parasitemia which were determined to be reinfection on Day 8 or later will be counted as responders for PCR corrected ACPR and as non-responder for PCR uncorrected ACPR from the day of test
- Presence of parasitemia which cannot be determined to be recrudescence or reinfection due to missing PCR data will be counted as non-responders from the day of test
- Missing/underdetermined responses at a visit due to missing blood smear data at the visit will be counted as non-responders (PCR corrected or uncorrected) unless there is a later blood smear test indicating no parasitemia
- Patients who received non rescue anti-malarial medication will be considered in the analysis as if they had not taken the antmalarial drug

In addition, PCR-corrected and uncorrected ACPR rate will be calculated and plotted using the Kaplan-Meier method for each treatment group in the FAS (see [Section 2.5.4](#)).

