Assuming that about 16% of patients will be excluded from the per-protocol analysis set, about 325 patients (50:50:50:50:50:25) will be randomized to yield 42 patients for each KAF156/LUM-SDF dose combinations and 21 patients for the Coartem[®] cohort in the per-protocol analysis set.

Figure 3-1 Power to reject adequate clinical and parasitological response (ACPR) rate less than or equal to 80% based on 2-sided 95% CI by true rate

Part B

The primary objective for this part is to assess the safety and efficacy of the selected KAF156/LUM-SDF dose combination(s) adjusted for body weight in pediatric patients. For the primary efficacy variable of PCR corrected ACPR rate at Day 29 based on the per-protocol analysis set, a sample size of at least 41 patients will provide about 80% power or higher to reject the null hypothesis of at most 80% ACPR rate based on the lower limit of 2-sided 95% exact confidence interval if the true rate is 95% or higher for a KAF156/LUM-SDF dose combination. Since there is a 2:1 ratio between a KAF156/LUM-SDF dose combination group and the Coartem[®] cohort, the sample size in the per-protocol analysis set will be targeted to be 42 patients for each KAF156/LUM-SDF dose combination group and 21 patients for the Coartem[®] cohort. Assuming that 16% of patients will be excluded from the per-protocol analysis set, about 50 pediatric patients will be randomized to yield 42 patients for each KAF156 and LUM-SDF combination and 21 patients for the Coartem[®] cohort in the per-protocol analysis set.

4 Change to protocol specified analyses

None

5 Appendix

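### The SAP leaves other-species reinfections out of uncorrected ACPR failure, which the protocol includes, and does not declare the change; the rate can only be equal or higher

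*SAP*

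**What the plan says.** **Protocol.** Section 9.5.1.1 sets the rule for uncorrected ACPR: "patients will be treated as failure on and after the visit when a new infection (i.e., reinfection) with" one of the named organisms. The clause names *P. falciparum* and then extends the rule beyond it, closing with the words "or other species is detected". Section 9.5.1.4 defines reinfection as asexual parasites that appear after the initial infection has cleared.

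**SAP, binary analysis.** The Note in 2.1.1.1 states that only the *P. falciparum* "asexual form is used for parasitemia/parasite in the assessments of treatment failure and ACPR". Section 2.1.1.2 builds uncorrected ACPR on failures defined in that way: "A patient is considered as non-responder at Day X if the patient experiences an ETF, LCF from Day 5 to Day X, or LPF" (within its own window). Section 2.7.2.1 still treats reinfection "as non-responder for PCR uncorrected ACPR from the day of test", but the mention of other species has gone.

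**SAP, Kaplan-Meier analysis.** Section 2.5.4.2 takes patients who are not already non-responders. Those who cleared the initial infection by Day 7 and are then infected with a different species "will be censored at the time of re-infection".

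**Declared changes.** SAP Section 4, headed "Change to protocol specified analyses", has the single entry None.

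**The concern.** The two documents define a listed secondary endpoint differently, and the SAP, which governs the programming, does not say so. Uncorrected ACPR at Days 15, 29 and 43 is in the objectives table of both documents. At Day 29 it is also one of the endpoints reviewed in the Part A interim assessment (Protocol 3.1; SAP 2.15).

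The affected cases are foreseeable. Protocol Section 4 expects about 85% of patients from Africa and the rest from Asia. Protocol 1.1 describes *P. vivax* as the dominant species in most countries outside sub-Saharan Africa. Protocol 9.5.1.1 itself gives treatment of *P. vivax* as an example of antimalarial use during the study.

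At stake is whether the reported uncorrected rate is the one that the protocol defines. A reader comparing report with protocol would not be told of the narrower definition.

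**Working it through.** **1. Denominators.** The documents give no figure for uncorrected ACPR, so the only planned figures to reproduce are the arm sizes in Protocol 9.8. With 16% excluded from the PPS, 42 / 0.84 = 50 per combination arm and 21 / 0.84 = 25 for control. The total is 6 × 50 + 25 = 325, which matches the plan. I use 50 and 25 as FAS sizes (assuming that nearly all randomized patients enter the FAS) and 42 as the PPS size.

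**2. Direction.** Take a patient with a film at the visit in question and cross the two facts that matter:

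| *P. falciparum* failure | New other-species infection | Protocol 9.5.1.1 | SAP 2.1.1.1–2.1.1.2 |
|---|---|---|---|
| No | No | Responder | Responder |
| No | Yes | **Failure** | **Responder** |
| Yes | No | Failure | Non-responder |
| Yes | Yes | Failure | Non-responder |

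Only the second row differs, and no row differs the other way. On this rule the SAP rate is never below the protocol-defined rate.

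**3. Size.** Let k be the number of second-row patients in an arm of n. Then SAP rate − protocol-defined rate = k/n. Because the documents do not give k, I show an assumed range of 0 to 5:

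| k | n = 50 (FAS, combination arm) | n = 25 (FAS, control) | n = 42 (PPS, combination arm) |
|---|---|---|---|
| 0 | 0 points | 0 points | 0 points |
| 1 | 2.0 | 4.0 | 2.4 |
| 2 | 4.0 | 8.0 | 4.8 |
| 3 | 6.0 | 12.0 | 7.1 |
| 5 | 10.0 | 20.0 | 11.9 |

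Example: 50 patients with 5 *P. falciparum* failures. The SAP rate is 45/50 = 90.0% (exact 95% CI 78.2 to 96.7). With k = 2 the protocol-defined rate is 43/50 = 86.0% (73.3 to 94.2).

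**4. Where the effect falls.** The FAS carries the full effect. In the PPS, patients given another antimalarial before Day 29 without treatment failure are excluded (Protocol 9.1; SAP 2.2 and Table 5-10). There, k counts only other-species cases that were untreated or were treated from Day 29 on.

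**5. Comparison with control.** The exploratory difference from Coartem changes by the difference between the two arms' k/n values, so it can move either way. With one such patient in each arm, the protocol rule lowers the combination arm by 2 points and control by 4. The difference then moves by 2 points in favour of the combination.

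**6. Is the SAP text really that narrow?** Section 2.5.4.2 supports this reading. If an other-species infection already made a patient a non-responder, there would be nobody of that kind left to censor among patients who are not non-responders.

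**7. Can the protocol rule be applied?** Yes. Protocol 6.4.1 requires the species to be noted when a follow-up film shows one other than *P. falciparum*.

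**The case against.** **SAP wording is not uniform.** Section 2.7.2.1 keeps reinfection as non-response for uncorrected ACPR, and 2.5.4.1 uses reinfection to include other species. One could argue that the protocol rule survives. But 2.7.2.1 speaks of parasitemia, which the Note limits to *P. falciparum*, and 2.5.4.2 fits only the narrow reading. Loose terminology is part of the problem and does not remove it.

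**The protocol disregards drugs given for *P. vivax*.** Section 9.5.1.1 analyses such patients as if the drug had not been taken. That clause deals with the drug, for both versions of ACPR. The species clause deals with the infection, for uncorrected ACPR only. Both can apply.

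**A SAP sensitivity analysis already covers it.** This is partly right. Section 2.7.2.2 makes FAS patients non-responders for uncorrected ACPR at Day 29 if they received non-study antimalarials, or certain prohibited drugs, before then without treatment failure. That captures other-species cases treated before Day 29. It misses untreated cases and Days 15 and 43, and it also counts patients given such drugs for other reasons.

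**The Kaplan-Meier analysis breaks no protocol rule.** This stands. The protocol plans Kaplan-Meier only for PCR-corrected ACPR, where 9.4.4 itself censors other species. The uncorrected version is a SAP addition. A reader might infer that censoring there contradicts the protocol, but no event rule exists for it to contradict.

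**A *P. falciparum*-only endpoint may suit a *P. falciparum* trial.** Possibly, but the change then has to be declared.

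**Conclusion.** The mismatch is real and undeclared, and it acts in one direction on each arm's rate. The SAP's binary uncorrected ACPR at Days 15, 29 and 43 equals the protocol-defined rate or exceeds it by k/n. This rests on reading the SAP Note as written and on k, which the documents do not supply.

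Three stronger readings are tempting but unsupported:

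- **That the SAP rate is higher.** It is higher only if k is at least 1 in the arm; with k = 0 the two rates are identical.
- **That the shift can be estimated from Asian recruitment.** The expected 15% of 325 is about 49 patients, but the documents give no rate of other-species infection among them. Any percentage-point figure built on that share rests on an invented rate.
- **That the choice of Part B cohorts turns on it.** The only efficacy criterion in Protocol Table 3-2 is PCR-corrected ACPR at Day 29. Secondary parameters may be looked at if needed. Uncorrected ACPR at Day 29 is reviewed at the interim assessment but has no threshold, and SAP 2.7.2 sets no hypotheses for secondary endpoints.

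The primary test and the sample size are untouched. The point should be corrected because it concerns fidelity to a listed secondary endpoint.

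**What to change.** **Preferred.** In SAP 2.1.1.2 and 2.7.2.1, count a new infection with asexual parasites of any *Plasmodium* species, after clearance of the initial infection, as non-response for uncorrected ACPR from the visit of detection. Limit the Note in 2.1.1.1 to match. Keep all three conditions (new, asexual, after clearance). A rule that counted any species seen from Day 8 would go beyond the protocol and could sweep in gametocyte carriage. Keep the *P. falciparum*-only rate as a labelled sensitivity analysis.

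**Alternative.** Keep the SAP definition, declare the change with its reason in Section 4, and report the protocol-defined rate alongside.

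**Either way.** In 2.5.4.2, align the handling of other species with the binary definition, or state that censoring them differs from it.

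**Cost.** SAP wording and one derivation, with no new data. The uncorrected rate may become slightly less favourable.

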2.1.1.2 Definition of ACPRs

Uncorrected ACPR at Day X where X=15, 29, or 43

- A patient is considered as non-responder at Day X if the patient experiences an ETF, LCF from Day 5 to Day X, or LPF from Day 8 to Day X.
- A patient is also considered as non-responder if the parasite is not cleared by Day X unless the patient discontinues the study prior to Day X without ETF or LCF or LPF, in which case the response is considered as missing.
- A patient is considered as responder (Uncorrected ACPR) at Day X if the patient is not classified as a non-responder at Day X and the patient has a malaria blood film showing absence of parasite at Day X or later if Day X is missing.
- The response for a patient is considered as missing/underdetermined if the patient is not classified as a non-responder and the malaria blood film result at Day X is missing and not followed by a subsequent negative result.

PCR-corrected ACPR at Day X where X=15, 29, or 43

- A patient is considered as non-responder at Day X if the patient experiences an ETF or LCF from Day 5 to Day 7.
- A patient is also considered as non-responder if the parasite is not cleared by Day X unless the patient discontinues the study prior to Day X without ETF or LCF or LPF, in which case the response is considered as missing,
- A patient is considered as non-responder at Day X if the patient has a parasite recrudescence from Day 8 to Day X
- A patient is considered as responder (corrected ACPR) at Day X if the patient is not classified as a non-responder by Day 7 and has a new infection or negative results from Day 8 to Day X based on PCR genotyping unless that the patient did not have parasites cleared prior to the new infection, in which case the patient is considered as non-responder.
- A patient is considered as responder at Day X if the patient is not classified as a non-responder at Day X and the patient has a malaria blood film showing absence of parasite at Day X or later if Day X is missing.
- The response for a patient is considered as missing/underdetermined if
 - The patient, not classified as non-responder at Day X, has parasite present from Day 8 to Day X for which the PCR genotyping of recrudescence or new infection is not determined.
 - The patient is not classified as a non-responder at Day X and the malaria blood film result at Day X is missing and not followed by a subsequent negative result.

Note - The outcome of PCR-corrected ACPR and uncorrected ACPR at a given day is categorized as responder or non-responder to distinguish from failure used in early treatment

failure, late clinical failure or late parasitological failure. With this notation, ACPR rate is the proportion of responders.

Recurrence of parasitemia after 7 days is considered as non-responder for uncorrected ACPR. We reclassify such patient as responder for PCR-corrected ACPR if recurrence of parasitemia after 7 days is due to new infection. Whether the recurrence of parasitemia after 7 days is due to recrudescence or new infection is determined and provided by the central laboratory. Negative PCR will categorize the patient as PCR corrected responder.

The above definitions of ACPRs are purely based on the malaria blood film and PCR results without consideration for taking concomitant anti-malaria drugs. In statistical analyses, some responses may be overridden for patients who take concomitant anti-malaria drugs (see [Sections 2.5 and 2.7](#)).

Fever Clearance is defined (in patients with axillary temperature of $\geq 37.5^{\circ}\text{C}$ at baseline) as the time of the first measurement of at least 2 consecutive axillary temperatures of $< 37.5^{\circ}\text{C}$ (or $< 38.0^{\circ}\text{C}$ for alternative routes) measured at least 24 hours apart.

Time to parasite clearance (PCT) is defined as time from the first dose until the first total and continued disappearance of asexual parasite forms which remained at least a further 48 hours

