### 9.4.1 Primary Variable(s)

The primary efficacy variable is the PCR corrected Adequate Clinical and Parasitological Response (ACPR) at Day 29.

A patient is considered as PCR-corrected ACPR at Day 29 if the patient does not meet any of the criteria of early treatment failure (up to Day 4), late clinical failure (Day 5 to Day 29) or late parasitological failure (Day 8 to Day 29), and is absence of parasitaemia on Day 29 irrespective of axillary temperature unless the presence of parasitaemia after 7 days is due to reinfection based on PCR.

A presence of parasitaemia after 7 days of treatment initiation (Day 8 or later) is considered as a reinfection only if the parasitaemia is clear before Day 8 and none of the parasite strain(s) detected on Day 8 or later matche with the parasite strain at baseline based on PCR genotyping.

Treatment failures after 7 days due to reinfection based on PCR genotyping are not considered as failure for PCR-corrected analyses but will be considered as failure for PCR uncorrected analyses.

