#### **9.5.1.4 Recrudescence and reinfection**

Reinfection is defined as appearance of asexual parasites after clearance of initial infection with a genotype different from those parasites present at baseline. Reinfection must be confirmed by PCR analysis.

Recrudescence is defined as appearance of asexual parasites after clearance of initial infection with a genotype identical to that of parasites present at baseline. Recrudescence must be confirmed by PCR analysis.

Incidence rates of recrudescence and reinfection at Days 15, 29 and 43 will be estimated by Kaplan-Meier method based on the subset of FAS patients who have clearance of initial infection by Day 7. Time to event (recrudescence or reinfection) will be calculated from the

time of first study medication to the date of first event if a patient experience the event and be censored at the time of last parasite assessment if a patient does not experience the event.

The following additional analyses will be performed for each part and the pooled Part A and Part B:

- For PCR corrected and uncorrected ACPR rates, the 95% confidence intervals for the difference between each test group (KAF156/LUM-SDF combination) and the control (Coartem®) will be provided using the Wilson uncorrected method. For the pooled analysis, the treatment differences versus control will be evaluated using a Mantel-Haenszel estimate of the common risk difference stratified by Part (see SAS manual version 13.2 Pages 2681-2682, 2014).
- For PCT and FCT, the difference between each test group and control will be evaluated using a log-rank test. Patients who did not experience a clearance will be censored at the time of last relevant assessment (parasite or fever). For the pooled analysis, the log-rank test will be stratified by Part.

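### The SAP loosens the protocol's primary endpoint in two ways (later parasite clearance allowed; film-positive, PCR-negative recurrence scored as response), while SAP Section 4 declares no change

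*SAP*

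**What the plan says.** **Protocol.** Section 9.4.1 defines PCR-corrected ACPR at Day 29 as the absence of early treatment failure, "late clinical failure (Day 5 to Day 29) or late parasitological failure (Day 8 to Day 29"), with no parasitaemia at Day 29. The only exception is parasitaemia after 7 days that PCR attributes to reinfection. Later parasitaemia "is considered as a reinfection only if the parasitaemia is clear before Day 8 and none of the parasite strain(s) detected on Day 8"; the sentence then rules out any match with the baseline strain. Section 9.5.1.4 defines reinfection as "appearance of asexual parasites after clearance of initial infection with a genotype different from those parasites present at baseline" and requires PCR confirmation. Section 6.4.1 makes the blood film the definitive test for a positive *P. falciparum* infection.

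**SAP.** Section 2.1.1.2 sets the clearance condition differently: "A patient is also considered as non-responder if the parasite is not cleared by Day X unless the patient discontinues the study". For Day 29 that moves the limit from before Day 8 to Day 29. A responder may also be a patient who "has a new infection or negative results from Day 8 to Day X based on PCR genotyping", provided parasites had cleared before the new infection. The note to the section adds "Negative PCR will categorize the patient as PCR corrected responder". The outcome is missing if the patient "has parasite present from Day 8 to Day X for which the PCR genotyping of recrudescence or new infection is not determined". The recrudescence label comes from outside the SAP: "Whether the recurrence of parasitemia after 7 days is due to recrudescence or new infection is determined and provided by the central laboratory".

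The revision history records the clearance change on 13-02-2019 and the negative-PCR change on 5-03-2019. SAP Section 4 reads None.

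**The concern.** The SAP redefines the primary endpoint, and the section meant to declare departures from the protocol says there are none. A reader of the study report who relies on Section 4 would take the reported ACPR to be the protocol's.

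The endpoint carries weight. Protocol Table 3-2 requires an exact lower limit above 80% on PCR-corrected ACPR at Day 29 before a cohort goes into Part B in children. Both rules push in the same direction, because each can only turn a non-response (or an unclassifiable outcome) into a response.

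The classification is also left open in two places:

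- **Day 8 persisters.** SAP 2.7.2.4 defines recrudescence as reappearance after clearance, which a patient who has never cleared cannot show. How the laboratory should label a same-strain Day 8 sample from such a patient is not stated.
- **Negative PCR.** SAP Table 5-10 excludes from the per-protocol set (PPS) patients whose Day 8 to Day 29 parasitaemia, after earlier clearance, cannot be called recrudescence or new infection. Read literally, that could remove the same PCR-negative patient whom 2.1.1.2 counts as a responder.

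**Working it through.** **1. The definitions side by side**

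| Patient | Protocol 9.4.1 / 9.5.1.4 | SAP 2.1.1.2 |
|---|---|---|
| Film-positive Day 8, never cleared before, same strain, film-negative by Day 29 | Failure: not reinfection, as not clear before Day 8 | Non-responder if labelled recrudescence; missing if genotyping is undetermined; responder if labelled otherwise or PCR-negative |
| First clears after Day 8, then a different strain before Day 29 | Failure: clearance came too late | The later new infection no longer counts against the patient; the result turns on how the Day 8 sample is labelled |
| Cleared, then film-positive between Day 8 and Day 29, PCR negative | Not a confirmed reinfection, so the exception does not apply | Responder |

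The first change therefore acts mainly through laboratory labelling. The second acts directly.

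**2. Does any planned analysis restore the protocol rule?**

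- The two sensitivity analyses in SAP 2.5.4 exclude patients with new infections. They leave both rules in place.
- The FAS rules in SAP 2.5.4 re-score missing PCR or missing film data, not a negative PCR.
- The Kaplan-Meier event in SAP 2.5.4.1 is the SAP's own PCR-corrected non-responder.
- Uncorrected ACPR at Day 29, reviewed at the interim, fails both groups. It also fails true new infections, so it cannot show the size of these two changes.

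**3. The plan's own figure**

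Inputs from Protocol 9.4.2 and 9.8: null rate 80%, 2-sided 95% Clopper-Pearson interval, 42 PPS patients per KAF156/LUM-SDF arm, true rate 95%, stated power at least 80%.

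The lower limit for x of n is the 2.5% quantile of Beta(x, n − x + 1). The smallest passing count at n = 42 is 39. Power = P(X ≥ 39 | n = 42, p = 0.95) = 0.843, so the plan's figure reproduces.

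**4. How far the pass mark is from one patient**

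| Responders / PPS | Lower limit | Table 3-2 |
|---|---|---|
| 37/42 | 74.4% | fail |
| 38/42 | 77.4% | fail |
| 39/42 | 80.5% | pass |
| 38/41 | 80.1% | pass |
| 39/43 | 77.9% | fail |

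- Failure to response inside the PPS: 38/42 becomes 39/42, fail to pass.
- Failure to exclusion from the PPS: 38/42 becomes 38/41, fail to pass.
- The opposite direction: SAP 2.2 criterion (d) keeps in the PPS patients with parasitaemia on Day 8 or later who had not cleared before Day 8. One additional never-cleared patient, a non-responder, turns 39/42 into 39/43, pass to fail.

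**5. How often an arm sits one short**

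P(X = 38 | n = 42) is 20.4%, 17.0% and 10.0% for true rates of 90%, 93% and 95%. These are chances of being at the margin, not chances that these rules alter a result. No reclassification rate is assumed, because the documents give none.

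**The case against.** **The first change has little demonstrated effect.** A Day 8 persister labelled recrudescence is still a non-responder, and one with undetermined PCR is missing. A new infection without prior clearance is also a non-response. This stands as a limit on size. It does not remove the textual difference, or the missing rule for labelling a persister. The revision history states that the aim was to let late clearers, and patients with missing data on Days 8, 9 or 15, be classified as cured. Only the late-clearance part is in question.

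**The second change fills a gap.** The protocol has no explicit rule for film-positive, PCR-negative samples and does not say whether a negative result is a valid evaluation under its PPS definition. Protocol 6.4.3 gives PCR a role in confirming microscopy on samples taken at withdrawal. If a negative PCR is not valid, the protocol would normally exclude the patient rather than count a failure. The contrast is then 38/41 (80.1%, pass) with 39/42 (80.5%, pass), or 37/41 (76.9%, fail) with 38/42 (77.4%, fail), so nothing flips at n = 42. For final sizes from 36 to 50, a move from exclusion to response flips the result only at n = 41 (37/40 at 79.6% to 38/41) and n = 48 (43/47 at 79.6% to 44/48 at 80.02%). This is a fair limit on the arithmetic. But failure and exclusion are the two readings the protocol supports. A negative PCR does not confirm a different genotype, and 6.4.3 concerns species confirmation, so neither reading makes the patient a cure.

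**Nothing is concealed.** Both changes are dated in the revision history, and the documents do not show that results by arm had been seen. That stands. A revision history tracks SAP edits, however, and Section 4 is where departures from the protocol are declared.

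**Any exact-binomial cut-off can be crossed by one patient.** True. The numbers show sensitivity, not an observed effect.

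**Conclusion.** The concern holds. Current SAP text departs from current protocol text on the primary endpoint in two respects, Section 4 declares neither, and no planned PCR-corrected analysis applies the protocol definition.

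The number of patients affected is unknown. At the planned 42 per arm, one patient counted as a failure under the protocol and a response under the SAP is enough to cross the Table 3-2 limit. That rests on the PCR-negative or late-clearing patient staying in the PPS. If the protocol would exclude a PCR-negative patient instead, scoring that patient as a response changes no verdict at 42, although it still does at 41 and 48.

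Two further limits apply. Cohort selection also uses safety and secondary endpoints, and PPS criterion (d) can work in the opposite direction. The point should be fixed, but it does not by itself invalidate the dose selection.

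**What to change.** 1. Replace None in SAP Section 4 with both changes and the reason for each.
2. Add an analysis of PCR-corrected ACPR at Day 29 scored by protocol 9.4.1: parasitaemia on Day 8 or later is non-response unless PCR shows a new infection after clearance before Day 8, and film-positive with negative PCR is not a response. It could be the primary analysis only if set before database lock. The last SAP history entry is after final lock, so the realistic route is a labelled sensitivity analysis beside the SAP-rule result.
3. State how a same-strain Day 8 sample without prior clearance is classified, whatever label the laboratory gives.
4. State whether a negative PCR is a valid evaluation, and align SAP 2.2 and Table 5-10 with the answer. If it is not valid, show the result with these patients excluded as well as counted as failures.
5. Report, per cohort, the number of patients reclassified under each rule.

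The cost is a short Section 4 entry and one additional derivation from data already collected. The PCR-corrected rate may come out slightly lower.
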